3.2 SECONDARY OBJECTIVES AND ESTIMANDS

Secondary Objective(s)

To assess the tolerability and reactogenicity profile of COVOVAX in comparison with the Control vaccine for COVISHIELD Prime, and COVAXIN Prime cohorts, separately

Estimand Description (including Endpoints)

nd Estimand 2 (for 2 and 3 listed below) of Estimand 3 (for 1 and 4 listed below)

Proportion of participants with at least one

- 1. Solicited local and/or Systemic adverse event up to 7 days post-vaccination
- 2. Unsolicited AE up to 28 days post-vaccination
- 3. SAE throughout study duration post-vaccination
- 4. Adverse event of special interest post-vaccination

A treatment policy strategy is used for assessing safety irrespective of use of immune-modifying medications/vaccinations.

An intercurrent event death will use strategy as follows:

CONFIDENTIAL Page 32 of 94

Secondary Objective(s)

Estimand Description (including Endpoints)

- Composite strategy is used for event death in case of SAE
- Solicited local and/ or systemic adverse events, unsolicited adverse events and AESI will use while on treatment strategy (i.e. data until death is utilized)

An intercurrent event COVID-19/SARS-CoV-2 infection will use Treatment policy for all listed above.

Endpoint:

- 1. Occurrence of solicited local and systemic adverse events (AEs) for 7 days post-vaccination
- 2. Occurrence of unsolicited AEs for 28 days postvaccination
- 3. Occurrence of SAEs, and adverse events of special interest (AESI) throughout the study duration following vaccination

To assess immunogenicity of Estimand 4 the COVOVAX booster dose in comparison with the Control vaccine by anti-S IgG and neutralizing antibody assays for COVISHIELD Prime. and COVAXIN Prime cohorts.

separately

GMTs and GMFR of anti-S IgG antibodies at 28, 90 and 180 days post-vaccination.

Principal stratum and Hypothetical strategy are used to understand antibody levels achieved through vaccination, without subsequent COVID-19/SARS-CoV-2 infection or use of any immune-modifying medications or other vaccines. While on treatment strategy is used for event death.

Endpoint:

Anti-S IgG antibodies at Day 29, Day 91 and Day 181

Estimand 5:

GMTs and GMFR of nAbs at 28 and 180 days postvaccination.

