10. STATISTICAL CONSIDERATIONS

10.1 OVERVIEW AND GENERAL CONSIDERATIONS

This is a Phase 3, observer-blind, randomised, active controlled study in adults aged ≥ 18 years in India who have already received primary vaccination against COVID-19 at least 6 months ago (6 months / 180 days from the second dose), to evaluate the immunogenicity and safety of the COVOVAX booster dose in comparison with the control vaccine (COVISHIELD and COVAXIN, for COVISHIELD and COVAXIN Prime cohorts, respectively).

A detailed statistical analysis plan will be created and finalized prior to database lock. All statistical analyses will be performed using SAS® software Version 9.4 or later. Additional details for statistical analysis will be included in the SAP.

Medical History and AEs will be coded using the Medical Dictionary for Regulatory Activities (MedDRA) (version 23.0 or later). The frequency count and percentage of participants will be summarized by system organ class (SOC) and preferred term (PT). Study participant-wise data listing will be provided.

Non-inferiority of COVOVAX booster over an active control vaccine group for each cohort will be concluded if both the lower limit of the two-sided 95% CI for the GMT ratio (GMR) >0.67 and the lower limit of the two-sided 95% CI for the difference in proportions of participants with ≥2-fold rise is >-10% for both anti-S IgG and nAbs between COVOVAX and the Control vaccine groups at Day 29. For consistency two-sided 95% confidence intervals (CIs) will be provided throughout. The main purpose of the safety analysis is to estimate the incidence rate of different events in each vaccine group.

No statistical tests will be performed at any interim analyses of safety data.

CONFIDENTIAL Page **60** of **94**

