	duration following vaccination 4. Adverse events of special interest (AESI) throughout the study duration following vaccination			group using two sided 95% Clopper-Pearson confidence intervals. This analysis will be performed for each cohort separately.	
	A treatment policy strategy is used for assessing safety irrespective of use of immune-modifying medications/vaccinations. An intercurrent event death will use strategy as follows: Composite strategy is used for event death in case of SAE Solicited local and systemic adverse events, unsolicited adverse events and AESI will use while on treatment strategy (i.e. data until death is utilized)				
	An intercurrent event COVID-19/SARS-CoV-2 infection will use Treatment policy for all endpoints listed above.				
Estimand 4, Estimand 5 (Secondary)	GMTs and GMFR of anti-S IgG antibodies at 28, 90 and 180 days post-vaccination.	Per protocol Population	Values below the limit of quantification (LOQ) or limit of detection (LOD) will be replaced by LOQ/2 and	MMRM will be fitted to the log transformed anti-S IgG and nAb with terms for vaccine group, visit, log baseline titer, age, sex, duration between 1 st - 2 nd	
	GMTs and GMFR of nAbs at 28 and 180 days post-vaccination.		LOD/2, respectively	vaccine dose, duration between 2 nd dose to booster dose of vaccine with interactions	

Page 76 of 94

			Main Estin	nation	Sensitivity Analysis
Estimand Label	Estimand Description	Analysis Set	Imputation/ Data/ Censoring Rules	Analysis Model/Method	
	Principal Stratum and Hypothetical strategy are used to understand antibody levels achieved through vaccination, without subsequent COVID- 19/SARS-CoV-2 infection or use of any immune-modifying medications or other vaccines. While on treatment strategy is used for event death.			for treatment by visit. The repeated timepoints on subject will be modelled (Details of the covariance structure will be provided in the SAP). Individual mean and 95% CI values by treatment from this model will be used to generate the geometric mean titers (GMTs) for anti-S IgG and nAb with at each time point by back transforming to the original scale. GMFRs will be provided descriptively for: anti-S IgG antibodies at 28, 90 and 180 days post-vaccination, nAb at 28 and 180 days post-vaccination. This analysis will be performed for each cohort separately.	

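### The secondary titre MMRM holds the baseline slope equal at Days 29, 91 and 181; adding log baseline titre by visit would guard the Day 181 GMTs at almost no cost

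*Protocol*

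**What the plan says.** In the statistical methods table (Protocol 10.6.3), the row for Estimands 4 and 5 starts its model as follows: "MMRM will be fitted to the log transformed anti-S IgG and nAb with terms for vaccine group, visit, log baseline titer, age, sex". It then adds the two dosing intervals. The interaction wording runs over a page break: "dose to booster dose of vaccine with interactions" is followed by "for treatment by visit. The repeated timepoints on subject will be modelled (Details of the covariance structure will be provided in the SAP". No covariate is crossed with visit.

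The one item that this row expressly leaves for later is the covariance structure: "Details of the covariance structure will be provided in the SAP". Section 10.1 has a general deferral: "Additional details for statistical analysis will be included in the SAP".

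The anti-S IgG endpoint is "Anti-S IgG antibodies at Day 29, Day 91 and Day 181"; nAbs are measured at Days 29 and 181 only. Per-arm GMTs at each visit are back-transformed from this model, and GMFRs are descriptive. The analysis set is per protocol, and Section 10.5.5 drops data from time points after a SARS-CoV-2 infection or an interfering medication or vaccine. Multiple imputation is stated in the co-primary GMR row but not in this one.

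**The concern.** How strongly the pre-booster titre predicts the titre four weeks after a booster need not equal how strongly it predicts the titre at six months. A single slope is then a compromise across visits.

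With complete data that compromise leaves the GMTs unbiased and only adds noise. It matters more when participants with later data differ in baseline titre from those without. The model fills in the missing Day 181 titres from baseline and from the earlier visits, and a wrong Day 181 slope carries the baseline imbalance into the Day 181 GMT. The exclusion of post-infection data makes such dependence plausible, because infection risk may be related to titre. What is at stake is the model-based GMT per arm that describes persistence, which is a stated summary for these estimands.

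**Working it through.** **Scale, from the plan's own figures.** The protocol gives no figure for the MMRM or for Day 181. Its Day 29 power (Section 10.4) reproduces:
- CV 1.1 gives a log-scale SD of sqrt(ln(1 + 1.1²)) = sqrt(ln 2.21) = 0.8905.
- With 79 evaluable per arm, SE = 0.8905 × sqrt(2/79) = 0.1417.
- −ln 0.67 = 0.4005, and 0.4005/0.1417 − 1.96 = 0.867, so power is 80.7% (normal) or 80.2% (noncentral t). The plan states 80%.

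**Direction.** Let b be the common slope, b181 the true Day 181 slope, and d the mean log baseline of those observed at Day 181 minus that of all analysed participants. The log-GMT error has the sign of (b181 − b) × d. It vanishes if the slopes are equal, or if d is zero on average (nobody missing, or missing at random with respect to baseline).

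**Simulation inputs, all assumed.** 79 per arm, three visits, baseline log SD 0.9, residual log SD 0.8, AR(1) residual correlation 0.6, unstructured covariance by maximum likelihood, 400-500 trials per scenario. A slope of 0.4 implies a total SD of sqrt(0.8² + 0.4² × 0.9²) = 0.877, close to the planning value of 0.8905. For the rows marked baseline-dependent, logit P(missing) = a − k × standardised baseline. With a = −2.4 (Day 91) and −1.9 (Day 181) and k = 1, 25% are missing at Day 181. With a = −1.5 and −1.0, 43% are missing.

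**Day 181 results.** GMT factors are estimate over truth. The variance ratio is common slope over slope by visit, for the treatment contrast.

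| Slopes, Days 29/91/181 | Missing at Day 181 | GMT, common slope | GMT, by visit | Variance ratio |
|---|---|---|---|---|
| 0.3/0.3/0.3 | 25%, baseline-dependent | 1.000 | 1.001 | 0.994 |
| 0.4/0.45/0.5 | 25%, baseline-dependent | 1.012 | 0.999 | 0.989 |
| 0.2/0.45/0.7 | none | 0.997 | 0.997 | 1.093 |
| 0.2/0.45/0.7 | 25%, baseline-dependent | 1.069 | 1.004 | 1.067 |
| 0.2/0.45/0.7 | 43%, baseline-dependent | 1.119 | 1.000 | 1.114 |
| 0.7/0.45/0.2 | none | 0.999 | 0.999 | 1.090 |
| 0.7/0.45/0.2 | 25%, baseline-dependent | 0.938 | 0.997 | 1.131 |
| 0.7/0.45/0.2 | 43%, baseline-dependent | 0.894 | 1.002 | 1.087 |

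Milder slopes of 0.2/0.35/0.5 with baseline-dependent missingness gave common-slope factors of 1.040 and 1.044 in the two arms, against 1.002 and 1.005 by visit. With completely random missingness and differing slopes, the factors stayed at about 1.00-1.01 under both models and only the variance rose (2-9%).

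**Lower missingness.** A second simulation with the same SDs and correlation used 10-15% missing at Day 181. The excess GMT bias of the common-slope model was about 1% for slopes 0.3/0.4/0.5, 2-3% for 0.2/0.4/0.6 and 3-4% for 0.1/0.4/0.7. At 28% missing these became about 2.5%, 5% and 7%.

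**Between-arm ratio.** With the same missingness mechanism in both arms, the Day 181 GMRs from the two models agreed to within 0.004 in every scenario. When only the control arm had baseline-dependent missingness, the common-slope GMR factors were 0.962, 0.968 and 1.062, against 1.001, 1.017 and 1.010 by visit.

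**The case against.** A common baseline slope is a legitimate parsimonious choice, and the same restriction applies to age, sex and the two dosing intervals. The SAP is not barred from adding a term, given the general deferral in Section 10.1. A reader might infer from the row that everything but the covariance structure is closed; the documents do not go that far. But an SAP that follows the listed terms carries the restriction forward. Where the protocol wants covariates left open it says so, as in the rows for Estimands 6 to 9. So this is a stated model that can be improved, not a missing detail.

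The sizes are also open to challenge. The only planning figure for loss is at most 15% non-evaluable. Swabs after vaccination are taken only for symptoms or contact (Section 7.3), which narrows the post-infection route to exclusion. The MMRM conditions on observed earlier titres, so loss driven by those titres is already handled under MAR. The simulated SE of the Day 181 log GMT was 0.10-0.12, so the upper 95% limit lies a factor exp(1.96 × 0.10) = 1.22 to exp(1.96 × 0.12) = 1.27 above the estimate. A bias of a few percent sits well inside that. Unadjusted GMTs for all four arms are also reported under Estimands 6 to 9.

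All of this stands, and it is why the severity is low. It does not remove the point, because the better model costs almost nothing.

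**Conclusion.** The point holds conditionally. As written, the MMRM imposes one baseline slope on all visits. Precision is lost only if the true slopes differ by visit: about 1-14% in the variance of a Day 181 contrast, under the slopes assumed. Bias needs a second condition, later missingness that depends on baseline. The per-arm Day 181 GMTs are then off by roughly 1-4% at 10-15% missing and 4-7% at about 25%, upward or downward according to how the slopes change. The protocol gives no slopes, baseline SD or Day 181 missingness, so these are illustrations and not estimates for this trial.

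Three stronger readings are not supported:
- **That the model loses precision as such, or that missing later data alone bias the GMTs.** With equal slopes the two models perform alike, and completely random missingness produced no bias.
- **That the vaccine comparison is at risk.** The Day 181 ratio is essentially unaffected unless missingness differs by arm. This row sets no test at Day 91 or Day 181, and the Day 29 non-inferiority decision comes from a separate ANCOVA.
- **That the variance penalty is large.** One simulation with slopes of 0.1/0.4/0.7 gave 31%, but that is a sevenfold change that nothing in the protocol suggests, and it concerns a contrast that this row does not specify.

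**What to change.** In the Estimand 4 and 5 row of Section 10.6.3, list log baseline titre by visit next to treatment by visit, and carry the same term into the SAP. For anti-S IgG this replaces one slope by three (two extra parameters); for nAbs it replaces one by two (one extra). At 79 evaluable per arm that is negligible, and with equal slopes the simulated variance ratio was 0.99-1.00. No change to design, sample size, visits or the co-primary analysis is needed.

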10.6.4 Analysis of Demographic and Baseline Characteristics

Demographic (age, gender, height, weight) and baseline characteristics (medical history, Preexisting conditions, and Prior medications) will be presented descriptively by vaccine group.

The quantitative variables will be summarized as mean, standard deviation, median, minimum and maximum and categorical variables will be summarized as frequency and percentage. Distributions of participants by gender, age will be summarized as frequency and percentages by cohort and within each cohort as overall and by vaccine group.

Baseline characteristics such as medical history, pre-existing conditions will be tabulated by vaccine group within each cohort using MedDRA dictionary classification and prior and concomitant medications will be tabulated by vaccine group within each cohort separately using WHODD drug classification.

10.6.5 Statistical Methods for Co-Primary Objectives

Statistical Method for the Co-primary endpoints

A summary of the statistical methods for the co-primary objectives are presented in the section 11.5.3 of the protocol.

To assess the primary objectives, the following non-inferiority hypotheses will be tested on the GMT of anti-S IgG antibodies and nAbs at 28 days (Day 29) post study vaccination.

1) Hypothesis testing for GMR:

 H_0 : $GMT_T/GMT_C \le 0.67$ (Inferior)

 H_1 : $GMT_T/GMT_C > 0.67$ (Non-inferior)

Where – T- COVOVAX and C -COVISHIELD or COVAXIN in the relevant cohort

The lower limit of the 95% CI will be compared with the non-inferiority margin 0.67 and COVOVAX will be declared non-inferior to the active control vaccine, COVISHIELD or COVAXIN in each cohort if > 0.67.

Confidential Page 80 of 94

2) Hypothesis testing for difference of proportions of participants with ≥2-fold rise

 H_0 : P_T - $P_C \le -10\%$ versus

 $H_1: P_T-P_C > -10\%$

Where – _T- COVOVAX and _C -COVISHIELD or COVAXIN in the relevant cohort.

The lower limit of the 95% CI for the difference in proportion will be compared with a non-inferiority margin of -10% and COVOVAX vaccine will be declared non-inferior to the Control vaccine (COVISHIELD or COVAXIN) if the lower limit > -10% on both anti-S IgG antibody and nAbs.

Version: 4.0 Dated 21 Apr 2022

10.6.6 Statistical Methods for Secondary and Exploratory Objectives

Immunogenicity analysis of neutralizing antibodies (nAbs), anti-S IgG antibodies and cell-mediated immune responses.

A summary of the statistical methods and sensitivity analysis for the immunogenicity objective (Estimand 4, 5, 6, 7, 8 and 9) is presented in the section 11.5.3 of the protocol. Summary of statistical methods for cell-mediated immune response (Estimand 10) is presented in the section 11.5.3 of the protocol.

In addition to the proposed analysis in section 11.5.3, the GMTs and GMFRs from baseline will be summarized with descriptive statistics including a boxplot (on log scale) versus time for each cohort separately.

10.6.7 Safety Objectives

Analysis of Solicited and Unsolicited Adverse Events

A summary of the statistical methods for the analysis relating secondary objective of safety, tolerability and reactogenicity profile (Estimand 2 and 3) is presented in Section 11.5.3 of the protocol.

In addition to above proposed analysis, the following summaries will be provided.

All solicited AEs will be summarized according to defined severity grading scales. Frequencies and percentages of participants experiencing each AE will be presented for each symptom severity. Summary tables showing the occurrence of any local or systemic AE overall will also be presented.

CONFIDENTIAL Page 81 of 94

Solicited local and systemic adverse events reported until 7 days post-vaccination will be summarized by maximal severity and by vaccine group within each cohort. All the solicited reactions occurring up to 7 days after each vaccination will be summarized similarly.

All unsolicited AEs reported until 28 days post-vaccination, assessed either as related or not related to vaccine by the investigator, will be recorded. The original verbatim terms used by investigators to identify AEs in the eCRFs will be mapped to PTs using MedDRA. The AEs will then be grouped by MedDRA PTs into frequency tables according to SOC. All reported AEs, as well as AEs assessed by the investigator as related to vaccine, will be summarized according to SOC, PT within SOC, and severity.

Safety and tolerability of study vaccines will be evaluated using the following endpoints:

- Number and severity of solicited local and systemic adverse events (AEs) and relatedness of all solicited systemic adverse events during the first 7 days after each vaccination.
- Number, severity and relatedness of all unsolicited AEs through 28 days after vaccination.
- Number, severity and relatedness of all SAEs through the entire study period.
- Number, severity and relatedness of all AESIs through the entire study period.

Generally, safety evaluations will be descriptive in nature. Tabular summaries of safety data will be provided for each vaccine group within each cohort.

Occurrence of local and systemic reactogenicity within 7 days after vaccination, as well as AEs through 28 days after vaccination and SAEs and AESIs during the entire study period, will be reported for all vaccine groups within each cohort.

Data listings of all adverse events will be provided by participant.

Additional details of the safety analysis such as (vital, physical examination. Etc.), disposition demographic will be provided in the statistical analysis plan.

10.6.8 Handling of Dropouts and Missing Data

Details for the imputation of missing values will be documented in the SAP based on details outlined in Section 11.5.3.

CONFIDENTIAL Page 82 of 94

11. QUALITY CONTROL AND QUALITY ASSURANCE

11.1 PRE-STUDY DOCUMENTATION

Prior to enrolment of participants at the study site, specific regulatory documents must be available, such as regulatory (DCGI) and Institutional Ethics Committee (IECs) approvals; curriculum vitae for investigator and study staff; standard operating procedures (SOPs) and other essential documents. Sponsor/designee will inform the investigator which documents need to be provided according to the applicable regulatory requirements.

Version: 4.0 Dated 21 Apr 2022

11.2 MONITORING

Sponsor monitoring responsibilities will be provided through qualified and appropriately trained individuals designated by CRO to carefully monitor all aspects of the study. A site initiation visit will be conducted prior to the beginning of the study and monitoring will be conducted during and at closeout of the study by the study monitor.

During the course of the study, the monitors will visit the clinical sites at intervals in order to verify that:

- The data are authentic, accurate and complete
- The safety and rights of participants are being protected
- The study is conducted in accordance with the approved protocol (and any subsequent amendment), GCP and all applicable regulatory requirements

Monitors will periodically contact the site and perform site visits. The extent, nature and frequency of site visits will be decided before the start of the study and will be based on considerations as study objectives, study design and complexity, and enrolment rate. During these contacts, the monitor will:

- Check and assess the progress of the study
- Review study data collected
- Perform source data verification, identify any issues and address their resolution

Monitoring will be conducted according to ICH-GCP. The individuals responsible for monitoring the study will have access to all records necessary to ensure the integrity/validity of the recorded data and will periodically review the progress of the study.

CONFIDENTIAL Page 83 of 94

The investigator must agree to allow the monitor direct access to all relevant documents and to allocate his/her time and the time of his/her staff to the monitor to discuss findings and any relevant issues.

The monitor must contact the site prior to the start of the study to discuss the protocol and data collection procedures with the site personnel.

The investigator should allow representatives of the Ethics Committee, Regulatory Authority and the sponsor to visit the study site.

11.3 DATA MANAGEMENT AND PROCESSING

Site PI is responsible for ensuring timely completeness and accuracy of data reported. Data collection is the responsibility of clinical trial staff at the study site under supervision of site PI. The CRO is responsible for clinical data management activities, including quality review, analysis and reporting of study data according to SOPs.

11.3.1 Data Collection

Data will be entered electronically by site study staff using Internet in eCRF. The data system will include password protection. Instructions for use of the system will be included in eCRF manual.

Clinical data will be entered directly from source documents. All source documents should be completed in neat and legible manner to ensure accurate interpretation of data. All information required by the study protocol must be entered into eCRF. An explanation must be provided for any missing data. Source documentation supporting the eCRF data should document the dates and details of study procedures, AEs and participant status. PI/site staff will maintain information in eCRFs and all source documents that support the data collected from each participant.

Study monitor will check for completeness and accuracy of eCRF during the monitoring visits.

